### 2. Accrual

For this trial, we project that we will screen ~1000 HIV/AIDS patients over 54 months (allowing six months to complete follow-up), 77% of whom will be current smokers ( $n = 770$ ). Additional data indicate that upwards of three-quarters of these patients will want to quit smoking and will want to use a medication in their quit attempt (Drach et al., 2010), yielding a sample of ~575 patients to recruit. Based on past varenicline trials ([name] et al., 2011; Patterson et al., 2009) and the present inclusion/exclusion criteria, we expect ~two-thirds of these patients to be eligible for the trial ( $n = \sim 345$ ). To be conservative, given the possible health problems evident in this population of smokers, we will project  $\leq 20\%$  of participants will withdraw from the trial and  $\geq 80\%$  of subjects will complete follow-ups. As is advised in smoking cessation trials (Hughes et al., 2003), intent-to-treat will be used for primary analyses, with missing outcome data coded as smokers.

### 3. Key Inclusion Criteria

Eligible subjects will be males and females:

1. 18 years of age or older who self-report smoking at least 1 cigarette (menthol and non-menthol) per day, on average.
2. Diagnosed with HIV infection and exhibiting viral load of  $\leq 1000$  copies/mL within the last 6 months.
3. Exhibiting CD4+ count of  $\geq 200$  cells/mm^3 within the last 6 months.
  1. If the participant has not had a CD4+ count test completed in the last 6 months, an older result ( $\geq 200$  cells/mm^3) may be used if evidence is provided that all subsequent viral loads results are  $\leq 1000$  copies/mL.
4. Able to use varenicline safely, based on a medical evaluation including medical history and psychiatric evaluation.
5. Residing in the geographic area for at least 7 months.
6. Women of childbearing potential (based on medical history) must consent to use a medically accepted method of birth control (e.g., condoms and spermicide, oral contraceptive, Depo-Provera injection, contraceptive patch, tubal ligation) or abstain from sexual intercourse during the time they are taking study medication and for at least one month after the medication period ends.
7. If current or past diagnosis of bipolar disorder (I, II, or NOS), eligible if:
  - a. No psychotic features
  - b. MADRS: total score  $\leq 8$  (past 4 weeks), suicidal item score  $\leq 1$  (past 4 weeks)
  - c. Y-MRS: total score  $\leq 8$  (past 4 weeks), irritability, speech content, disruptive, or aggressive behavior items score  $\leq 3$  (past 4 weeks)
  - d. No psychiatric hospitalization or Emergency Room visits for psychiatric issues in the past 6 months

- e. No aggressive or violent acts or behavior in the past 6 months
- 8. Able to communicate fluently in English.
- 9. Capable of giving written informed consent, which includes compliance with the requirements and restrictions listed in the combined consent/HIPAA form.

#### **4. Key Exclusion Criteria**

Subjects who present with and/or self-report the following criteria will not be eligible to participate in the study.

##### Smoking Behavior

- 1. Current enrollment or plans to enroll in another smoking cessation program in the next 7 months.
- 2. Regular (daily) use of chewing tobacco, snuff, snus, cigars, cigarillos, or pipes.
- 3. Current use or plans to use nicotine substitutes (gum, patch, lozenge, e-cigarette) or smoking cessation treatments in the next 7 months.
  - a. Note: Once participants are found eligible for the study, they are told they should refrain from using any nicotine replacement therapy (NRT) for the duration of the study. If a subject reports NRT use during the study, s/he may be permitted to continue pending approval from the study physician and PI.

##### Alcohol/Drug Exclusion Criteria

- 1. Current untreated and unstable diagnosis of substance dependence. Current untreated and unstable diagnosis of substance abuse requires Study Physician approval.
  - a. Note: The participant is eligible if dependence was in the past (greater than 1 year ago) or if the participant is currently receiving treatment (e.g. medication, group therapy, support groups and/or intensive outpatient programs) and has been stable for  $\geq 30$  days.
- 2. Breath Alcohol Concentration (BrAC) assessment greater than or equal to 0.01 at the Intake Session.

##### Medication Exclusion Criteria

Current use or recent discontinuation (within last 14 days) of the following medications:

- 1. Other smoking cessation medications (e.g. Zyban, Wellbutrin, Wellbutrin SR, Chantix)
  - a. Note: Once participants are found eligible for the study, they are instructed to only use the smoking cessation medication provided to them by the study staff. If a subject reports using a non-study smoking cessation medication, the study physician and PI will evaluate the situation and determine if it is safe for the subject to continue participation.
- 2. Anti-psychotic medications (if used to treat psychotic symptoms. Other uses may be eligible pending physician approval).

##### Medical Exclusion Criteria

- 1. Women who are pregnant, planning a pregnancy within the next 7 months, or lactating.
- 2. Current diagnosis of unstable and untreated major depression, as determined by self-report & MINI.
  - a. Note: The participant is eligible if stable for  $\geq 30$  days (stability is defined by the use of mood regulating medication and/or by receiving regular mental health care evaluations or therapy).
- 3. Current or past diagnosis of psychotic disorder, as determined by self-report or MINI.
- 4. History of unstable heart disease, stroke, myocardial infarction, angina, or tachycardia (if stable, requires Study Physician approval).
- 5. Uncontrolled hypertension (SBP  $> 160$  or DBP  $> 100$ ).
  - a. Note: If a participant presents with blood pressure greater than 160/100 at sessions occurring on Week 0 (Pre-Quit) or at any other point during the treatment period, they will not be provided with/able to continue on medication unless the study physician grants approval.
- 6. History of seizures or current seizure disorder that is unstable and untreated. (If seizures are stable and treated, requires Study Physician approval.)
- 7. History of decompensated cirrhosis (i.e., a diagnosis of hepatic decompensation, decompensated cirrhosis, end-stage liver disease, ascites, variceal hemorrhage, spontaneous bacterial peritonitis,

hepatic encephalopathy) as determined by medical history review is subject to study physician approval.

8. Evidence of severe renal impairment including current dialysis treatment, estimated creatinine clearance <30 mL/min (within 6 months of enrollment) or eGFR <60 mL/min/1.73m^2 (within 6 months of enrollment).
9. Previous allergic reaction to varenicline.

**Suicide Hx Exclusion Criteria**

1. Any suicide attempt or suicidal behavior within 2 years of enrollment
  - a. Note: Any participant that reports a suicide attempt or episode of suicidal behavior more than 2 years before enrollment will be evaluated by senior clinical staff ([name] or [name]) to assess final eligibility based on the complete psychological profile ascertained at the intake session.
2. Current suicidal ideation (within the last 30 days of enrollment)
3. Two or more lifetime suicide attempts or episodes of suicidal behavior
4. If the participant has a history of bipolar disorder, any suicide risk score on the MINI or self-reported lifetime suicide attempt or suicidal behavior

**General Exclusion Criteria**

1. Any medical condition or concomitant medication that could compromise subject safety or treatment, as determined by the Principal Investigator and/or Study Physician.
2. Inability to provide informed consent or complete any of the study tasks as determined by the Principal Investigator and/or Study Physician.

**5. Vulnerable Populations**

Children, pregnant women, fetuses, neonates, or prisoners are not included in this research study.

**6. Populations vulnerable to undue influence or coercion**

Educationally or economically disadvantaged persons are included but not solely targeted for recruitment. Cognitively impaired persons are not included in the current study. Because of our recruitment efforts for this study, it is possible that University of Pennsylvania employees and students may be invited to participate. Status of participation in the study will be independent of the subject's work or school activities.

**7. Subject Recruitment**

Participants will be recruited from the Infectious Disease practices at the Hospital of the UPENN, Presbyterian Hospital, and Pennsylvania Hospital. [name] will oversee the integration of this study into the clinics, ensuring access to participants, collection of medical data (through UPHS PennChart medical record reviews and laboratory result requests), and access to private consulting rooms for screening at the CFAR clinics. These practices see over 500 patients monthly and more than 200 new patients each year.

After obtaining the necessary training and clinic clearances to access PennChart for participating UPHS clinics, Research Assistants (RAs) will review the electronic medical records to identify potential subjects on a weekly basis (each site has patient smoking status indicated on the record). Individual medical records will be evaluated for eligibility based on the inclusion and exclusion criteria for this study. Daily clinic schedules will be ascertained and RAs will approach patients prior to or after consultation or treatment at the clinic. In addition to in-clinic recruitment, RAs will contact potentially eligible patients (after EMR review) by telephone based on their clinic provider's specified research contact preference. Providers may choose one of the following contact options: 1) all patients identified as initially eligible may be contacted 2) all patient records identified as initially eligible will be sent to the provider via PennChart for review and approval prior to contact 3) all patient records identified as initially eligible may be sent to the provider, who assumes full responsibility and discretion regarding the research contact (no contact may be made by the research staff). Those patients deemed eligible for contact will be contacted by telephone. RAs will introduce the research study and the collaboration

between the researchers, infectious disease clinic, and the patient's provider. After assessing the patient's interest, HIV status, and smoking status, the patient will then be provided with additional study information and an opportunity to assess his/her intake eligibility based on a screening questionnaire.

Research Recruitment Best Practice Advisories (BPAs) will also be integrated into electronic medical record recruitment. BPAs are designed to fire passive alerts within PennChart at the point of care, notifying providers that a patient may be eligible for a specific study. This specific BPA will evaluate if a patient meets specific criteria associated with the trial and will present the provider with the option to indicate if a patient is interested in participating in the study or not. This BPA will only present if the patient meets the initial screening criteria based on smoking status and problem list diagnoses and will only present in specified departments. This indication of interest only serves to trigger a notification to study staff that a patient has met initial screen criteria and further follow-up is requested to determine eligibility of the patient. This alert is a passive alert and will not interrupt the provider's workflow, but will be listed in the same section as other clinically warranted BPAs.

If our accrual rate is lower than anticipated based on our feasibility data, [name] and the CFAR CAB will use their connections with community-based HIV/AIDS organizations in the Delaware Valley region to promote the trial and enhance accrual rates. The CFAR CAB, comprised of people with HIV/AIDS or professionals in the treatment of substance use among those with HIV, has numerous linkages to community-based organizations that can be used to enhance participant recruitment should that be necessary. We will also advertise the study using poster, newspaper, and internet based advertisements (this includes in-app advertising, Craigslist, and Twitter). Information about the study will be available on the CIRNA and iConnect websites. In addition, research staff will attend HIV/AIDS community events and community clinic intake hours to provide information about the study, distribute recruitment materials, and collect participant contact information via a secure, web-based data collection service. Additionally, we will place recruitment data requests with electronic research data warehouses such as Penn Data Store and Pennomics to obtain lists of pre-consented potential participants. ResearchMatch, a national health volunteer registry that was created by several academic institutions and supported by the U.S. National Institutes of Health as part of the Clinical Translational Science Award (CTSA) program, will also be utilized. ResearchMatch has a large population of volunteers who have consented to be contacted by researchers about health studies for which they may be eligible.

RAs and UPHS medical personnel will screen patients from UPENN and community based HIV/AIDS clinics to identify potentially eligible and interested participants by phone or in person. Participants recruited through other methods will also be screened by phone or in person. Participants who are eligible and interested in the study will be scheduled for an Intake session (Week -1) with research staff. At the Intake session the participant will sign an informed consent and HIPAA form, complete eligibility and baseline assessments, and be scheduled for Week 0. The participant's eligibility will be confirmed by Drs. [name], [name] and [name].

To ensure a high level of retention and adherence in this trial we will: 1) educate subjects about the benefits of protocol compliance; 2) schedule in-person sessions at convenient times (e.g., evenings); 3) use a medication adherence component in the counseling protocol (Gariti et al., 2009; [name] et al., 2008), and 4) as is standard practice in smoking cessation trials ([name] et al., 2010b; Niaura et al., 2005), provide modest financial compensation for session completion and transportation costs.

## STUDY DESIGN

### 1. Phase

This study is a Phase III clinical trial.

[figure not shown]
### 2. Design

This is a randomized, between-subject, double-blind, placebo-controlled study.

**Figure 1. Study Overview**

Version 19: February 13, 2018

Template Version: 7 May 2008

### 3. Study Duration

#### Length of Subject's Participation in Study

Subjects will participate in study related activities for approximately 7 months from initial eligibility assessment in the clinic through follow-up. A subject's length of participation may be affected by center or subject scheduling conflicts.

#### Projected date of completion of the proposed study

We expect to complete accrual in approximately 54 months, completing the trial in December 2016. We expect to obtain our numbers in this timeframe by enrolling approximately 6 subjects per month.

**Table 1. Study Timeline**

Tasks/Months	1	3	12	24	36	48	60
Refine and test DMS and Train Staff (1-3)	X	-----X					
Recruitment/baselines (3-54)		X	-----				X
Treatment (3-57)		X	-----				X
Outcome assessments (15-60)			X	-----			X
Analysis/manuscripts (48-60)					X	-----	X

## DRUGS OR DEVICES

#### *Study Medication*

##### *Dosing*

Varenicline will be used in accordance with FDA approved labeling: Day 1-Day 3 (0.5mg once daily); Day 4-Day 7 (0.5mg twice daily); and Day 8-Day 84 (1.0mg twice daily).

#### Supply, Preparation, Storage, Packaging and Dispensing of Study Medication

Varenicline and matching placebo, provided at no-cost by Pfizer, will be packaged and stored at the University of Pennsylvania Investigational Drug Service. Varenicline and matching placebo will be packaged into blister packs in 1-2 week supplies. Medication will be distributed to participants in increments at Weeks 0, 3, and 7.

IDS will oversee the randomization and labeling of all study medication, and will assign each kit, which contains 12 weeks of medication for one subject, and a unique Pharmacy Randomization Number (PRN). Once a new subject is enrolled and eligible, IDS will assign the subject the next available PRN. The research staff will then label the blister packs with the subject's study ID number. The PRN and study ID number must match for each blister pack a subject receives. Medication kits will be stored in a locked cabinet at our center until they are dispensed at participant medication pick-up visits.

Regular study drug reconciliation will be performed to document drug assigned, drug consumed, and drug remaining. This reconciliation will be logged on the drug reconciliation form, and signed by the research staff member who completed the reconciliation.

At the completion of the study, there will be a final reconciliation of drug shipped, drug consumed, and drug remaining. This reconciliation will be logged on the drug reconciliation form, signed and dated by the research staff. Any discrepancies noted will be investigated, resolved, and documented prior to return or destruction of unused study drug. Drug destroyed on site will be documented in the study files.

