### **Intake Session (Week -1): Consent, Eligibility Determination, Baseline Measures.**

Subjects who pass the pre-screening will be invited to attend a 2.5-hour Intake Session where the following activities will occur:

1. Subjects will hear a study description where all study procedures, risks, and information about the study medication will be reviewed. Subject questions will be answered. Following this presentation, the combined informed consent and HIPAA form will be completed.
2. A urine pregnancy test (all female subjects) will be administered.
3. A breath alcohol concentration assessment (BrAC) to control for alcohol consumption. The handheld device uses a disposable mouthpiece, reports the concentration of alcohol in breath and takes about 2 minutes.
4. A carbon monoxide (CO) breath assessment to control for prior tobacco exposure. The handheld device uses a disposable mouthpiece, reports CO in parts per million (ppm), and takes about 3 minutes.
5. Mental status examinations (Mini International Neuropsychiatric Interview, HADS, C-SSRS, and MADRS, YMRS, Bipolar Disorder Additional Screener, if necessary) with a trained research staff member.
6. Complete routine medical history, including blood pressure assessment.
7. A concomitant medication review.
8. Complete baseline paper and pencil measures to assess 1) background variables that may serve as covariates and will allow for the assessment of the study's external validity (e.g., smoking history, demographics), 2) mediators (e.g., affect, cognition), 3) moderators (e.g., disease-related information, and 4) baseline smoking behavior.
9. Provide one 10ml blood sample (2 teaspoons) to assess nicotine metabolite ratio (cotinine and 3-hydroxycotinine).
10. Provide one 10ml blood sample (2 teaspoons) for DNA collection and genotyping.

Initially eligible participants who have not had kidney function tests within the last 6 months (as ascertained by medical record review or provision of results from the participant's health care provider) will provide one 10ml blood sample (2 teaspoons) to complete these tests following the Intake Session. Test results that are outside of normal ranges will be reviewed for final eligibility by the Study Physician prior to enrollment.

If eligible at this point, subjects will be scheduled for the first treatment session (Week 0).

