**Varenicline or Placebo Treatment (Weeks 0-12).**

The dosing regimen used in past varenicline trials and consistent with FDA guidelines will be used: Day 1-Day 3 (0.5mg once daily); Day 4-Day 7 (0.5mg twice daily); and Day 8-Day 84 (1.0mg twice daily). Medication and matching placebo will be packaged into blister packs in 1-2 week supplies. Medication will be distributed in increments at Weeks 0, 3, and 7. Day 1 of study medication will be scheduled no more than 60 days following the Intake Session. If Day 1 is scheduled more than 60 days following the Intake Session, the participant will be required to attend another Intake Session in order to reaffirm eligibility. Participants who discontinue the study medication for 14 or more consecutive days will require approval from the Principal Investigator and Study Physician before restarting the study medication.

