#### Nicotine Metabolic Rate (3-HC/cotinine ratio) and Genes related to Nicotine Dependence

Two baseline blood samples will be collected at Intake and analyzed for nicotine metabolites to determine rate of nicotine metabolism. Nicotine is metabolized to cotinine and then to 3-HC by the P450 (CYP) 2A6 enzyme (Nakajima et al., 1996). The 3-HC/cotinine ratio is a stable measure of the rate of nicotine metabolism, which influences response to nicotine dependence treatments (Lerman et al., 2006; Patterson, [name] et al., 2008). Variation in 3-HC/cotinine and other genetic polymorphisms in nicotine metabolizing enzymes (CYP2A6) and in drug targets (CHRNA4, CHRN2, etc.) will also be explored for associations with therapeutic response to treatment. The biosamples of individuals who complete the Pre-Quit visit will be sent to the laboratory of [name] at the University of Toronto for analysis. These analyses will be exploratory.

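### The kit number that fixes the arm can be assigned before Week 0, so people who never attend Week 0 can enter the primary analysis as smokers; assigning it at Week 0 avoids this cheaply

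*Combined protocol and SAP*

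**What the plan says.** **Assignment.** Under Supply, Preparation, Storage, Packaging and Dispensing of Study Medication, the Investigational Drug Service (IDS) controls allocation: "IDS will oversee the randomization and labeling of all study medication". Each kit holds one subject's full 12 weeks of drug and carries a PRN, so the PRN determines the arm. The trigger is: "Once a new subject is enrolled and eligible, IDS will assign the subject the next available PRN". Staff then label the packs with the study ID, and the section goes on to say that kits stay in a locked cabinet at the centre until the medication visits. No visit is named for the assignment.

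**Eligibility.** The Intake Session section ends: "If eligible at this point, subjects will be scheduled for the first treatment session (Week 0". For people who need kidney function tests after Intake, abnormal results "will be reviewed for final eligibility by the Study Physician prior to enrollment".

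**First drug.** The Pre-Quit Session (Week 0) text dispenses the first three weeks of medication at that visit. The treatment section adds: "Day 1 of study medication will be scheduled no more than 60 days following the Intake Session". If the gap is longer, "the participant will be required to attend another Intake Session in order to reaffirm eligibility". Under Medical Exclusion Criteria, a blood pressure check at Week 0 can also hold back medication pending the study physician's approval.

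**Analysis.** The Accrual section specifies intent-to-treat "with missing outcome data coded as smokers". The Abstinence (primary) and Missing Data sections repeat the rule. No section defines the intent-to-treat set or makes an exception for people who are assigned a kit and never start.

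**Loss before Week 0.** The nicotine metabolism section treats Pre-Quit attendance as a separate step: "The biosamples of individuals who complete the Pre-Quit visit will be sent to the laboratory".

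**The concern.** If the arm is fixed before Week 0, some people will be randomised and then not attend the visit at which counselling and medication begin. Their outcome cannot depend on the arm, because they received nothing. They still take up part of the 310, and the missing-equals-smoking rule adds them as smokers to both denominators. The absolute difference in quit rates shrinks and power falls.

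This is avoidable. It comes from when the number is handed out, not from anything the trial needs in order to be randomised or blinded. The repeat Intake rule leaves a related gap: nothing says what becomes of a PRN already assigned when the 60 days run out, or of its holder if eligibility is not reaffirmed.

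**Working it through.** **Order of events as written**

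1. Intake: consent, assessments, eligibility, sometimes laboratory review afterwards.
2. Week 0 is scheduled once the person is eligible.
3. PRN assigned once the person is enrolled and eligible; packs labelled; kit stored until a medication visit.
4. Week 0: attendance, checks, first dispensing.

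Step 3 can fall any time from the eligibility decision to Week 0. Because labelling and storage follow assignment and precede dispensing, assignment before Week 0 is the natural reading. Intake is labelled Week -1, so the nominal gap is about a week. The 60 days run from Intake to Day 1 and are an upper limit on the gap between assignment and first dose.

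**Inputs**

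- 310 randomised (Abstract), half to varenicline (Risk/Benefit Assessment): 155 per arm.
- Two-sided z-test at 0.05 (Power).
- Planned quit rates (Power): Week 12, 21.2% vs 50.3%; Week 24, 14.5% vs 33.5%.
- Smallest difference considered (Power): 15 points. No base rate is given, so the planned placebo rates are used: 21.2% vs 36.2% and 14.5% vs 29.5%.
- Share *f* who never attend Week 0: not in the documents. Assumed range 0 to 20%, equal in both arms.

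**Formula**

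Power = Φ[(d − 1.96·SE0)/SE1], where d = p2 − p1, SE0 = √(2·p̄(1−p̄)/n), SE1 = √((p1(1−p1)+p2(1−p2))/n) and p̄ = (p1+p2)/2. With never-starters coded as smokers, each rate becomes p(1−f) while n stays at 155.

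**The plan's own figures first**

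- Week 12, 21.2% vs 50.3%: 99.98%, consistent with the stated >90%.
- Week 12, 15 points: d = 0.150, p̄ = 0.287, SE0 = 0.0514, SE1 = 0.0507. Power = Φ[(0.150 − 0.1007)/0.0507] = Φ(0.97) = 83.5%, or 80.1% with continuity correction, in line with the stated 80%.
- Week 24, 14.5% vs 33.5%: 97.8%. The stated 85% does not reproduce from its own inputs. It understates power and is a separate matter.

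**With never-starters counted as smokers**

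| f | People (of 310) | Wk 12, 21.2 vs 36.2% | Difference (points) | Wk 24, 14.5 vs 29.5% | Wk 12 planned | Wk 24 planned |
|---|---|---|---|---|---|---|
| 0% | 0 | 83.5% | 15.0 | 89.4% | 99.98% | 97.8% |
| 5% | 15.5 | 80.7% | 14.25 | 87.4% | 99.96% | 96.9% |
| 10% | 31 | 77.8% | 13.5 | 85.0% | 99.9% | 95.9% |
| 20% | 62 | 71.1% | 12.0 | 79.5% | 99.6% | 92.9% |

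For example, at f = 10% the Week 12 rates become 0.212 × 0.9 = 19.08% and 0.362 × 0.9 = 32.58%. Power = Φ[(0.135 − 1.96 × 0.0497)/0.0491] = Φ(0.76) = 77.8%. The 15-point Week 12 case drops below 80% at about 6% never-starters.

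**Effect measures.** The risk difference shrinks by the factor (1 − f) and the risk ratio is unchanged. The odds ratio, which the Aim 1 model reports, moves at f = 10% from 3.76 to 3.51 at the planned Week 12 rates and from 2.11 to 2.05 in the 15-point case.

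**What the timing of assignment buys (f = 10%, 15-point Week 12 case)**

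- Never-starters kept as smokers: 77.8%.
- Never-starters dropped and not replaced (139.5 per arm): 79.4%.
- Assignment at Week 0, so all 310 attended: 83.5%.

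The gain is 83.5 − 77.8 = 5.7 points. Of this, 1.6 come from removing the dilution and 4.1 from having 310 people who attended Week 0.

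**The case against.** The strongest reply is that the early assignment is inferred. The word *enrolled* is undefined, no visit is named, and assignment at Week 0 also fits the text. The intent-to-treat set is undefined too, so counting never-starters as smokers is a second inference. The biosample rule fits equally well with Pre-Quit being the point of entry, and Figure 1, which might show the randomisation point, is not visible in the text reviewed. All of this stands. A reader might infer that kits are in fact assigned up to 60 days before the first dose, and that every no-show is a treatment failure. The documents do not support that: they permit it without stating it, and the 60 days are counted from Intake.

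The size is also limited. The no-show share is assumed, and the loss matters only for the 15-point difference. A reader might infer that the trial is underpowered; at the planned effects it is not, even with 20% never-starters. The calculation treats the quoted rates as rates among starters. The Accrual section already projects up to 20% withdrawal, and if the quoted rates already absorb loss of this kind, part of the effect is counted twice.

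The plan partly anticipates the issue. The Missing Data section says its rule can attenuate the difference and adds a completers-only analysis. That analysis also drops people lost after treatment began, so it does not isolate loss before treatment and cannot replace a clean starting point.

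The change is also not entirely free. No-shows must be replaced, and this is Version 19, dated February 2018, after the projected completion in December 2016, so participants may already have been randomised.

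**Conclusion.** The point holds as a cheap improvement. The text allows the arm to be fixed after Intake and before Week 0, and it has no rule for someone who is assigned a kit and never attends. Such a person can be counted as a smoker in either arm. With blinding in place the result is dilution and lost power, not bias towards one arm.

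On the 15-point Week 12 difference the cost is 2.8 points of power at 5% never-starters (83.5 − 80.7), 5.7 at 10% and 12.4 at 20% (83.5 − 71.1). At the planned effects, power remains 99.6% at Week 12 and 92.9% at Week 24 even at 20%. These figures assume 155 per arm, equal no-show shares in the arms, every never-starter coded as a smoker, and the quoted rates applying to people who start. The range of shares is an assumption.

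**What to change.** In the drug supply section, replace the trigger with: IDS assigns the PRN at the Week 0 visit, once attendance and the existing Week 0 checks are complete and immediately before dispensing. State that this is the moment of randomisation, and that for participants randomised under this rule the 310 and the intent-to-treat set are counted from it. Anyone already randomised stays in the intent-to-treat set, whether or not they attended Week 0. With this trigger a repeat Intake no longer involves a PRN already assigned. Neither the randomisation nor the blind is affected, and no eligibility or treatment rule changes.

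**Cost.** IDS and staff must assign and label on the day of Week 0. The section mentions storage both at IDS and at the centre, so where unassigned kits are held should be confirmed. More eligible people must also pass Intake to reach 310 randomised: 310/0.95 ≈ 327 at 5% no-shows, 310/0.90 ≈ 345 at 10% and 310/0.80 ≈ 388 at 20%. The Accrual section projects about 345 eligible, so the projection covers no-shows up to about 10%.
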